following index BCS (Arm 1 and Arm 2).	suspected residual disease (patient-level analysis; Arm 1 and Arm 2).	# of patients in Arm 1 that underwent a 2 nd surgery on the ipsilateral breast within 1 year of index BCS # of patients in Arm 1 # of patients in Arm 2 that underwent a 2 nd surgery on the ipsilateral breast within 1 year of index BCS # of patients in Arm 2	x100%	
16. To characterize the impact of FGR on the rate of 2 nd surgery shortly after index BCS (Arm 1 and Arm 2).	Percentage of patients receiving an early 2 nd surgery (planned or actual) on the ipsilateral breast related to positive final margins prior to radiation or medical management (patient-level analysis; Arm 1 and Arm 2).	# of patients in Arm 1 that underwent or are scheduled to undergo a 2 nd surgery on the ipsilateral breast due to positive SoC final margins following initial BCS prior to radiation or medical management # of patients in Arm 1	x100%	Patient-level early reoperation rate.
		P(2.16b) Arm 2 only = # of patients in Arm 2 that underwent or are scheduled to undergo a 2 nd surgery on the ipsilateral breast due to positive FGR final margins following initial BCS prior to radiation or medical management # of patients in Arm 2	x100%	

SBI-CIP 20-002 Rev: v1.8 A prospective multi-center clinical study evaluating the use of PD G 506 A and the Eagle V1.2 Imaging System for the visualization of carcinoma during breast conserving surgery Page: 38 of 157	·
--	---

Secondary Objectives	Parameter Description	Parameter Formula	Abbreviated Description
17. To characterize the impact	Sum of the weight (mg) of all tissue	P(2.17a) =	Amount of tissue removed
of FGR during BCS on the	removed based on SoC compared to the	Mean SoC tissue weight (mg) Arm 1 and Arm	with FGR beyond SoC.
amount of tissue removed	sum of the weight (mg) of all tissue	2:	
(Arm 1 and Arm 2).	removed based on FGR (patient-level	SoC tissue weight = Primary specimen (mg) +	
	analysis; Arm 1 and Arm 2).	SoC-driven cavity shave specimen(s) (mg)	
		P(2.17b) =	
		Mean FGR tissue weight (mg) Arm 2 only:	
		Total tissue weight = FL-driven cavity shave	
		specimen(s) (mg)	
18.To characterize the impact	Patient satisfaction with the cosmetic	P(2.18a) =	Patient satisfaction.
of FGR during BCS on the	outcome of breast conserving surgery	Mean Breast-Q Breast Conserving Therapy	
patient-reported cosmetic	performed based on SoC in	Module satisfaction with breasts score before	

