Only data from participants in Part B will be used for the analyses of primary and secondary efficacy. Data from all participants in both Part A and Part B will be used for the evaluation of safety.

In Part B of the study, participants will be randomized in a ratio of 1:6 (Arm 1 [SoC]: Arm 2 [PD G 506 A]).

The randomization will be stratified by breast cancer type (invasive carcinoma with or without in situ carcinoma vs. in situ carcinoma alone). This will ensure an approximate ratio of 1:6 within each type of breast cancer. Preoperative diagnosis based on diagnostic tissue sampling performed during screening (e.g. percutaneous core needle biopsy, fine-needle aspiration cytology) will be

SBI-CIP 20-002 Rev: v1.8 A prospective multi-center clinical study evaluating the use of PD G 506 A and the Eagle V1.2 Imaging System for the visualization of carcinoma during breast conserving surgery	Page: 46 of 157
---	-----------------

used for stratification. Permuted blocks will be used to construct the randomization schedule and the randomization will be implemented using an interactive web response system.

Data from the SoC arm (Arm 1) will not be used for statistical analysis of the primary and most secondary endpoints. The purpose of the SoC arm is to compare resected tissue weight, patient reported cosmetic outcomes, re-excision prior to initiation of adjuvant therapies, re-excision within 1-year of index BCS, and safety between study arms as well as to minimize bias introduced into the SoC procedure if the *surgeon* is aware that they have an opportunity to revise the margins further after SoC is complete. A 3-month, 6-month and 1-year follow-up will be performed to evaluate patient reported cosmetic outcomes as well as the rate of re-excision across both study arms. The 6-month and 1-year follow-up data will be collected as an extension phase to the study, meaning database lock and analysis of all other endpoints will be performed following the last patient's 3-month follow-up data is collected. Analysis of 6-month and 1-year data will occur after the last patients 1-year visit. The clinical study report will be appended to include the 6-month and 1-year data, when available.

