15.7. Secondary and Exploratory Endpoint Analysis

Secondary and exploratory endpoints based on *patient-level* data will be analyzed using similar methods to the primary and key secondary endpoints, using Wilson (score) confidence intervals. Re-operation rates will be compared between treatments using Fisher's exact tests.

Secondary and exploratory endpoints based on *orientation-level, primary specimen-level, and point-level* data will be analyzed using a weighted estimator, proposed by Lee and Dubin (Lee and Dubin, 1994), which takes into account the correlation (clustering) of the margins within a patient. This method will be used to calculate the estimates and two-sided 95% confidence intervals.

Descriptive statistics will be used to summarize the weight of resected tissue specimens (SoC specimens vs. FGR specimens). Mean total tissue weight (Arm 1 vs. Arm 2) will be compared using a two-sample t-test.

Breast-Q survey results will be summarized using actual values and change from baseline values using descriptive statistics. The difference in change scores between Arm 1 and Arm 2 will be summarized descriptively and presented along with a 95% confidence interval on the difference in means. For the Breast-Q survey results at 3 months, if the lower bound of this confidence interval is \geq - 10 then non-inferiority will be claimed. Results at 6 months and 1 year will be described with summary statistics. For the analysis of Breast-Q survey results, the previously defined minimal important difference as the reference point for what patients consider a meaningful change in Breast-Q scores. The minimal important difference is defined as: "The smallest difference in score in a domain of interest that patients perceive as beneficial and which would mandate, in the

|--|

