absence of troublesome side effects and excessive cost, a change in the patient's (health care) management''⁷⁰. While patients in Arm 2 are anticipated to have marginally more tissue removed as a result of *FGR* as compared to SoC [analyzed in secondary endpoint P(2.16)], it is not anticipated that resection of this additional tissue will negatively affect the patient's satisfaction with the appearance of their breasts as compared to patients in Arm 1. For secondary endpoint 18 [P(2.18a) & P(2.18b)] we have defined a mean difference in change score \leq -10 (Arm 1 – Arm 2) as meeting our criterion for non-inferiority. Previous studies have reported a minimal important difference in Breast-Q scores of 7-8⁷¹ for the breast satisfaction subscale in breast reconstruction patients. To date there are no known publications addressing the minimal important difference using the Breast Conserving Therapy module of the Breast-Q survey. While a change score of \geq -10 would represent a negative change in breast satisfaction, this risk may still be considered acceptable to patients if the intervention is associated with improved clinical outcomes (e.g. decreased probability of having positive margins).

Depth of tumor analyses of tissue specimens identified by FL imaging will be summarized using descriptive statistics.

Exploratory subgroup analyses will be performed on key efficacy endpoints. Subgroups will include patients who underwent sentinel node mapping with blue dye injection vs. those who did not, and patients who underwent comprehensive circumferential shaves during surgery vs. those who had selective shaves during BCS.

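### P(2.17b) gives the name total tissue weight to the fluorescence-driven shaves alone, so the between-arm t-test of total tissue weight in 15.7 has no defined Arm 1 value and no defined sum for Arm 2

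*Combined protocol and SAP*

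**What the plan says.** Objective 17 in Section 7.2.2 concerns the effect of FGR on the amount of tissue removed, in both arms. It has two formulas.

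- P(2.17a), for Arm 1 and Arm 2, is the SoC tissue weight: primary specimen plus SoC-driven cavity shaves.
- P(2.17b) is headed "Mean FGR tissue weight (mg) Arm 2 only". Its formula line then reads "Total tissue weight = FL-driven cavity shave" specimens. The heading calls the quantity FGR weight; the formula calls it a total.

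Section 15.7 first describes the weights of SoC and FGR specimens and then adds a between-arm test: "Mean total tissue weight (Arm 1 vs. Arm 2) will be compared using a two-sample t-test". It also states the direction expected: "patients in Arm 2 are anticipated to have marginally more tissue removed". For that analysis it cites P(2.16).

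Section 8.1 makes this comparison part of the reason for having a control arm: "The purpose of the SoC arm is to compare resected tissue weight, patient reported cosmetic outcomes".

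**The concern.** A prespecified test should name a quantity that exists in both arms. The only quantity the protocol defines as total tissue weight is the fluorescence-driven increment, which Arm 1 patients cannot have. The sum that would answer the question, all tissue removed per patient in each arm, is not written anywhere.

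An analyst working from the formulas therefore has to choose. Some choices give an answer to a different question, and one gives an answer of the opposite sign. What is at stake is a stated purpose of the control arm and a check on the statement in Section 6.2.6 that the extra tissue is not expected to harm cosmetic outcome. It is a secondary endpoint outside the key set in 15.6.

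**Working it through.** There is no figure in the plan to reproduce: the documents give no mean, SD, sample size or power for tissue weight. The check is therefore of definitions, followed by an illustration on stated assumptions.

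**Step 1. What each arm has.**

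| Quantity | Arm 1 | Arm 2 |
|---|---|---|
| SoC tissue weight, P(2.17a) | primary specimen + SoC shaves | primary specimen + SoC shaves |
| Total tissue weight as labelled in P(2.17b) | not defined | fluorescence-driven shaves only |
| SoC + fluorescence-driven tissue | no formula | no formula |

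**Step 2. What the 15.7 test could then be.** Scale mean SoC weight to 1 in both arms; randomisation, and blinding of the surgeon until SoC is declared complete (8.3), support equal means. Let f be the mean weight of fluorescence-driven shaves as a fraction of SoC weight. The expected difference, Arm 2 minus Arm 1, is:

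- strict reading of the label: no Arm 1 value, so no test;
- P(2.17a) in Arm 1 against P(2.17b) in Arm 2: f - 1, negative whenever f < 1;
- P(2.17a) in both arms: 1 - 1 = 0, whatever FGR removes;
- all tissue in each arm: (1 + f) - 1 = f, always positive when any shave is taken.

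Only the last agrees with the direction stated in 15.7.

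**Step 3. Illustration.** Assumptions, not document figures: f from 0.05 to 0.30; coefficient of variation (CV) c of SoC weight from 0.5 to 1.0; CV of shave weight 1; shave and SoC weights independent. Arm sizes 72 and 428 are from 15.2, with two-sided alpha 0.05 from 15.1 and a normal approximation with unequal variances.

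- P(2.17a) against P(2.17b): z = (f - 1) / sqrt(c²/72 + f²/428).
- All tissue in each arm: z = f / sqrt(c²/72 + (c² + f²)/428).

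For c = 0.5 and f = 0.10:

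- first form: -0.90 / sqrt(0.25/72 + 0.01/428) = -0.90 / 0.0591 = -15.2;
- second form: 0.10 / sqrt(0.25/72 + 0.26/428) = 0.10 / 0.0639 = 1.57, power about 35%.

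| c | f | z, P(2.17a) v P(2.17b) | z, all tissue | Power, all tissue |
|---|---|---|---|---|
| 0.5 | 0.05 | -16.1 | 0.78 | 12% |
| 0.5 | 0.10 | -15.2 | 1.57 | 35% |
| 0.5 | 0.30 | -11.5 | 4.59 | over 99% |
| 1.0 | 0.05 | -8.1 | 0.39 | 6% |
| 1.0 | 0.10 | -7.6 | 0.78 | 12% |
| 1.0 | 0.30 | -5.9 | 2.34 | 65% |

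**Step 4. Patients with no fluorescence-driven shave.** Section 5.2 counts an imaged patient as having undergone FGR even when nothing is resected, and 15.4.1 assigns the mITT population to patient-level analyses. A sum over no specimens is naturally zero, but P(2.17b) does not say so, while 15.1 tabulates non-missing values and 15.4.1 provides for imputation. If a share s of Arm 2 has a shave and only those patients are averaged, the increment is overstated by a factor 1/s. The documents give no s.

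**Step 5. Cross-reference.** The P(2.16) cited in 15.7 for tissue weight is the early re-operation rate in 7.2.2. Tissue weight is P(2.17).

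**The case against.** The best reply is that the intention is clear. Section 15.7 separates a descriptive summary of SoC and FGR specimens from a test of total weight by arm. The second is distinct only if total has its ordinary meaning, and the expectation of marginally more tissue in Arm 2 needs the same meaning. Section 15.1 leaves further detail to a statistical analysis plan. This has force: a careful analyst would probably sum the specimens, and a result showing far less tissue in Arm 2 would be questioned at once. But it asks the analyst to override the only written definition. The description of endpoint 17 does not help, since it sets SoC tissue against FGR tissue and tags the comparison to both arms.

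Four stronger readings are tempting and are not supported.

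- A reader might infer that the plan literally tests lumpectomies against shaves. It does not: Arm 1 has no quantity under the label, and that pairing needs a differently named variable to be brought in.
- A reader might infer that a sign-reversed result is likely. It is a consequence of one possible pairing, and one that the text of 15.7 would expose.
- A reader might infer that the extra tissue goes unmeasured. P(2.17b) measures it directly within patient, since FGR starts only after SoC is declared complete.
- A reader might infer that the trial loses its only objective measure of cosmetic cost. Weight is a proxy; cosmesis is assessed by Breast-Q with a non-inferiority criterion in P(2.18), and P(2.10) and P(E.21) capture carcinoma-negative fluorescence-driven shaves.

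The point about zero weights is likewise a clarification. No text excludes patients without a shave, and no particular inflation factor can be given.

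**Conclusion.** The point holds as a mismatch between an endpoint formula and the test that uses its name. It is more than missing detail: no pairing of the two defined quantities estimates the between-arm effect of FGR on tissue removed. The signs in Step 2 need only equal mean SoC weight in the two arms and shaves lighter than the lumpectomy. The sizes (-0.95 to -0.70, 0, and +0.05 to +0.30 of SoC weight) and the z values rest wholly on the assumed f and CVs.

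The scope is limited to one non-key secondary endpoint. P(2.17b) stands as the increment within Arm 2; the primary analysis and sample size are untouched. It should be corrected before the analysis is run.

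**What to change.** - Relabel P(2.17b) as FGR tissue weight, and state that Arm 2 mITT patients with no fluorescence-driven shave have the value 0.
- Add P(2.17c), total tissue weight: primary specimen + SoC-driven shaves in Arm 1; primary specimen + SoC-driven shaves + fluorescence-driven shaves in Arm 2.
- State in 15.7 that the two-sample t-test compares P(2.17c) between arms.
- Correct the cross-reference in 15.7 from P(2.16) to P(2.17).

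The cost is wording in 7.2.2 and 15.7 and the matching entry in the statistical analysis plan. Section 12.4.4.2 already has every specimen except biopsies weighed individually, so P(2.17c) is a sum of recorded values. After the change, power for the between-arm test on the Step 3 assumptions still ranges from about 6% to over 99%. A non-significant result should therefore be reported alongside P(2.17b) and not read as showing that no extra tissue was removed.

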7.3. Exploratory Objectives and Endpoints

Exploratory Objective	Parameter Description	Parameter Formula		Abbreviated Description
19. To characterize the	Patient-level ex vivo diagnostic	P(E.19) Sensitivity =		Patient-level ex vivo specificity to
diagnostic performance	performance of PD G 506 A-induced	TP Patient (ex vivo)	x 100%	identify residual carcinoma after
of ex vivo imaging of	fluorescence to determine the	TP Patient (ex vivo) + FN Patient	X 100%	FGR is complete.
PD G 506 A to identify	presence or absence of residual	(ex vivo)		

SBI-CIP 20-002	Rev: v1.8	A prospective multi-center clinical study evaluating the use of PD G 506 A and the Eagle V1.2 Imaging System for the visualization of carcinoma during breast conserving surgery	Page: 39 of 157
-----------------------	--------------	--	-----------------

Exploratory Objective	Parameter Description	Parameter Formula		Abbreviated Description
malignant breast tissue (Arm 2 only).	cancer in the surgical cavity at the end of FGR as compared to the final margin histopathology.	P(E.19) Specificity = TN Patient (ex vivo) TN Patient (ex vivo) + FP Patient (ex vivo)	x 100%	
	Only FL-positive orientation- ex vivo and FL-negative orientation- ex vivo orientations are included in the patient-level diagnostic performance	P(E.19) PPV = TP Patient (ex vivo) TP Patient (ex vivo) + FP Patient (ex vivo)	x 100%	
	definitions for this analysis.	P(E.19) NPV = TN Patient (ex vivo) TN Patient (ex vivo) + FN Patient (ex vivo)	x 100%	
20. To determine the frequency with which PD G 506 A-induced fluorescence is visualized but that tissue is not resected	Percentage of patients who did not have a FL-guided shave although indicated by FL imaging.	P(E.20a) = #Patients with ≥ 1 FL-positive orientation where no FL- driven shave was resected #Patients with ≥1 FL-positive orientation	x 100%	Fluorescence-positive tissue that cannot be resected.
(Arm 2 only).		P(E.20b) = #Patients with ≥ 1 FL-positive orientation where no FL- driven shave was resected #Patients in Arm 2	x 100%	
		P(E.20c) Clinical outcomes (e.g., porfinal margin rate, need for 2 nd surger also be reported for patients ≥ 1 FL-1 orientation but the FL-driven shave(s resected	y) will positive	

SBI-CIP 20-002	Rev: v1.8	A prospective multi-center clinical study evaluating the use of PD G 506 A and the Eagle V1.2 Imaging System for the visualization of carcinoma during breast conserving surgery	Page: 40 of 157
-----------------------	--------------	--	-----------------

Exploratory Objective	Parameter Description	Parameter Formula		Abbreviated Description
21. To characterize the diagnostic performance of imaging of PD G 506 A to identify malignant breast tissue (Arm 2 only).	Percentage of FL guided shaves that had no cancer on histopathology.	P(E.21) = # FL-driven shave specimens with no carcinoma anywhere # of FL-driven shave specimens	x 100%	Carcinoma negative FL-driven shave specimens.
22. To investigate the depth of carcinoma tissue that can be visualized by PD G 506 A using the Eagle V1.2 Imaging System.	Depth of tumor identified by FL imaging relative to the inked surface, reported by tumor type (invasive carcinoma and DCIS), using descriptive statistics (e.g., mean, median, and range).			Depth of FL visualization.
23. To investigate the depth of carcinoma tissue that can be visualized by PD G 506 A using the Eagle V1.2 Imaging System.	Percentage of specimens where invasive carcinoma was located only below the inked surface (i.e., inked surface cancer free) for the surfaces imaged ex vivo (primary specimen or shave specimens) where FL detected invasive carcinoma.	P(E.23)= #FL-positive orientations-ex vivo where invasive carcinoma was located only below the inked surface (i.e., inked surface cancer free) #FL-positive orientations ex vivo with invasive carcinoma	x 100%	Fluorescence visualization of invasive carcinoma below the imaged surface.
24. To investigate the depth of carcinoma tissue that can be visualized by PD G 506 A using the Eagle V1.2 Imaging System.	Percentage of specimens where DCIS was only located deeper than 2 mm below the inked surface (i.e., DCIS not within 2 mm of the inked surface) for the surfaces imaged ex vivo (primary specimen or shaves) where FL detected DCIS.	P(E.24) = #FL-positive DCIS orientations- ex vivo where DCIS was only located deeper than 2 mm below the inked surface (i.e., DCIS not within 2 mm of the inked surface) #FL-positive orientations-ex vivo with DCIS	x 100%	Fluorescence visualization of DCIS > 2 mm below the imaged surface.

carcinoma during breast conserving surgery
--

Exploratory Objective	Parameter Description	Parameter Formula		Abbreviated Description
25. To characterize the diagnostic performance of imaging of PD G 506 A to identify malignant breast tissue (Arm 2 only).	For those primary specimens containing cancer anywhere on the bisected surfaces, the proportion that displayed fluorescence in any area/region. Primary specimen examination will only be conducted at a subgroup of clinical sites.	P(E.25)= # sectioned primary specimens with carcinoma anywhere and positive fluorescence anywhere # sectioned primary specimens with carcinoma anywhere	x 100%	Sensitivity of PD G 506 A to identify carcinoma inside the primary specimen.
26. To characterize the diagnostic performance of PD G 506 A using	Diagnostic performance of PD G 506 A-induced fluorescence to determine the presence or absence of cancer	$P(E.26) Sensitivity = \frac{TP}{TP + FN}$	x 100%	Diagnostic performance of PD G 506 A to detect cancer in the primary specimen.
the Eagle V1.2 Imaging System to identify malignant breast tissue	e Eagle V1.2 Imaging system to identify specimen. alignant breast tissue the primary specimen Primary specimen examination will	$P(E.26) Specificity = \frac{TN}{TN + FP}$	x 100%	
in the primary specimen (Arm 2 only).		$P(E.26) PPV = \frac{TP}{TP + FP}$	x 100%	
		$P(E.26) \text{ NPV} = \frac{\text{TN}}{\text{TN} + \text{FN}}$	x 100%	

SBI-CIP 20-002 Rev: v1.8 A prospective multi-center clinical study evaluating the use of PD G 506 A and the Eagle V1.2 Imaging System for the visualization of carcinoma during breast conserving surgery	Page: 42 of 157
---	-----------------

Exploratory Objective	Parameter Description	Parameter Formula	Abbreviated Description
27. To characterize the diagnostic performance of ex vivo imaging of PD G 506 A to identify malignant breast tissue (Arm 2 only).	Sensitivity, specificity, NPV, and PPV of ex vivo FL imaging of primary specimen margin surfaces and all cavity shave specimen(s) (SoC or FL-guided). SSO/ASTRO definitions of histopathology positive/negative will be used.	P(E.27) Sensitivity = TP Orientation (ex vivo) TP Orientation (ex vivo) + FN Orientation (ex vivo) P(E.27) Specificity = TN Orientation (ex vivo) TN Orientation (ex vivo) + FP Orientation (ex vivo) + FP Orientation (ex vivo)	Orientation-level ex vivo diagnostic performance for all specimens using SSO/ASTRO definitions (direct ground truth only).
		FP Orientation (ex vivo) $P(E.27) PPV = TP Orientation (ex vivo) $	
		P(E.27) NPV = TN Orientation (ex vivo) TN Orientation (ex vivo) + FN Orientation (ex vivo)	

SBI-CIP 20-002	Rev: v1.8	A prospective multi-center clinical study evaluating the use of PD G 506 A and the Eagle V1.2 Imaging System for the visualization of carcinoma during breast conserving surgery	Page: 43 of 157
-----------------------	--------------	--	-----------------

Exploratory Objective	Parameter Description	Parameter Formula		Abbreviated Description
28. To characterize the diagnostic performance of ex vivo imaging of PD G 506 A to identify malignant breast tissue	Sensitivity, specificity, NPV, and PPV of ex vivo FL imaging of the imaged surfaces of the primary bisected specimen as compared to the histopathology of the corresponding biopsies.	P(E.28) Sensitivity = TP primary specimen biopsy TP primary specimen biopsy + FN primary specimen biopsy	x 100%	Diagnostic performance inside the primary specimen.
(Arm 2 only).		P(E.28) Specificity = TN primary specimen biopsy TN primary specimen biopsy + FP primary specimen biopsy P(E.28) PPV = TP primary specimen biopsy TP primary specimen biopsy + FP primary specimen biopsy + FP primary specimen biopsy	x 100% x 100%	
		P(E.28) NPV = TN primary specimen biopsy TN primary specimen biopsy + FN primary specimen biopsy	x 100%	

SBI-CIP 20-002	Rev: v1.8	A prospective multi-center clinical study evaluating the use of PD G 506 A and the Eagle V1.2 Imaging System for the visualization of carcinoma during breast conserving surgery	Page: 44 of 157
-----------------------	--------------	--	-----------------

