Cavity Shave Specimen(s)	Tissue specimen(s) excised from the cavity after the primary specimen has been removed; cavity shave specimen(s) The surfaces of a cavity shave specimen are described with reference to the primary specimen (not relative to the cavity/patient). The outside surface of a cavity shave specimen is the surface that was continuous with the remaining breast tissue. The inside surface of a cavity shave margin is the surface that is continuous with most recently resected tissue.	
Primary Specimen	Also known as the "lump" or main mass refers to the primary piece of tissue resected during a standard of care lumpectomy. It contains most (or all) of the primary tumor mass	
	I. Shave: any tissue removed from the lumpectomy cavity walls after the main specimen is removed.	
Shave types (Excised	II. Standard of care (SoC) cavity shave: any piece of tissue excised from a specific location of the lumpectomy cavity wall after the primary specimen has been removed, as per surgeon's decision per SoC.	
tissue)	III. Fluorescence-driven shave specimen(s): any piece of tissues excised from a specific location of the lumpectomy cavity wall indicated by PD G 506 A-induced tissue fluorescence after SoC resection has been completed.	
c) Definit	ion of margins and re-excision	
Margin Assessment	The procedure(s) performed to evaluate the outside surface of the last resected tissue(s) and/or cavity. Given that FL-guided resection occurs after completion of SoC, margin assessment may be based on SoC methods (SoC margin assessment) or FL-imaging (FL margin assessment). SoC margin assessment may include WL palpation, visualization, specimen radiology and intraoperative ultrasound (patients undergoing intraoperative histopathological assessment are excluded from participating).	

SBI-CIP 20-002	Rev: v1.8	A prospective multi-center clinical study evaluating the use of PD G 506 A and the Eagle V1.2 Imaging System for the visualization of carcinoma during breast conserving surgery	Page: 17 of 157
-----------------------	--------------	--	-----------------

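### E.23 and E.24 (and E.22 on one reading) count carcinoma under any FL-positive surface as visualised, so false-positive fluorescence over tumour scores as depth of visualisation

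*Combined protocol and SAP*

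**What the plan says.** Section 7.3 gives three endpoints for the depth objective.

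- **E.22** has no formula. It is described as "Depth of tumor identified by FL imaging relative to the inked surface, reported by tumor type (invasive carcinoma and DCIS" and is to be summarised descriptively.
- **E.23** has as numerator "FL-positive orientations-ex vivo where invasive carcinoma was located only below the inked surface (i.e., inked surface cancer free" and as denominator "FL-positive orientations ex vivo with invasive carcinoma". The description limits it to surfaces "where FL detected invasive carcinoma", and its short label is "Fluorescence visualization of invasive carcinoma below the imaged surface".
- **E.24** has the same form. The denominator is "FL-positive orientations-ex vivo with DCIS", and the numerator is the subset whose DCIS lies only deeper than 2 mm.

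Both E.23 and E.24 include primary-specimen surfaces as well as shaves. Section 5.1 says of the primary specimen: "It contains most (or all) of the primary tumor mass". In Appendix 2 the surgeon gives one yes/no answer on red fluorescence for each anatomical surface. In Section 12.6.1 the pathologist records, for each primary-specimen surface, whether carcinoma is at ink and whether it is below ink, and, where carcinoma is present, its type or types and the shortest distance from ink. Section 15.7 adds only this: "Depth of tumor analyses of tissue specimens identified by FL imaging will be summarized using descriptive statistics".

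**The concern.** A depth of visualisation is a statement about detection: of the surfaces with tumour at a given depth, what fraction fluoresce, and is that more than fluoresce with no tumour there? E.23 and E.24 reverse the conditioning. They start from surfaces that fluoresced and ask where the tumour was. The formulas need only fluorescence and carcinoma on the same orientation, although the description of E.23 speaks of detection and the labels of visualisation. Nothing ties the fluorescent area to the tumour, caps the depth, or brings in FL-negative surfaces over tumour at the same depth.

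The result depends on where tumour sits relative to ink and on the false-positive rate. It also moves the wrong way: worse specificity raises it.

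There is a possible internal conflict as well. E.27 scores ex vivo surfaces by SSO/ASTRO margin status, under which an FL-positive, histology-negative surface is a false positive. The positive-margin text in Section 5.1 is incomplete in the copy read. If a negative margin means ink free of invasive carcinoma and no DCIS within 2 mm, the same surface can be an error in E.27 and a success in E.23 or E.24.

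At stake is any statement about depth. Appendix 4 allows study data to be used in publications, marketing and licence submissions.

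**Working it through.** The plan states no expected value for E.22 to E.24, so there is no figure of its own to reproduce. The check is a stress test: what does E.23 read for a dye that sees nothing below the surface?

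**Model.**

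- q: share of imaged ex vivo surfaces with invasive carcinoma at ink. Not in the documents; assumed 5%, varied from 2% to 20%.
- s: probability of an FL-positive call when carcinoma is at ink. Assumed 70%.
- f: probability of an FL-positive call otherwise, whatever lies beneath. Assumed 5%, varied from 2% to 10%.
- r: share of ink-negative surfaces with invasive carcinoma recorded below. Not in the documents; shown at 30% and 100%.

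For this dye, E.23 = (1−q)·r·f / [q·s + (1−q)·r·f]. The true proportion visualised below the surface is 0%.

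**Results at q = 5%, s = 70%** (so q·s = 0.035):

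| f | r = 30% | r = 100% |
|---|---|---|
| 2% | 0.0057/0.0407 = 14% | 0.0190/0.0540 = 35% |
| 5% | 0.01425/0.04925 = 29% | 0.0475/0.0825 = 58% |
| 10% | 0.0285/0.0635 = 45% | 0.0950/0.1300 = 73% |

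**Varying q at f = 5%, s = 70%:**

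| q | r = 30% | r = 100% |
|---|---|---|
| 2% | 0.0147/0.0287 = 51% | 0.0490/0.0630 = 78% |
| 10% | 0.0135/0.0835 = 16% | 0.0450/0.1150 = 39% |
| 20% | 0.0120/0.1520 = 8% | 0.0400/0.1800 = 22% |

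**Accuracy from the protocol's earlier study.** Table 6.1 reproduces: sensitivity 13/20 = 65.0% and specificity 22/26 = 84.6% at 15 mg/kg; 15/22 = 68.2% and 20/25 = 80.0% at 30 mg/kg. These imply f = 4/26 = 15.4% and 5/25 = 20.0%. At q = 5%:

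- r = 100%: 82% and 85%.
- r = 30%: 0.0438/0.0763 = 57% and 0.0570/0.0911 = 63%.

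That table comes from biopsies and a different device, so it shows only that 5% false positives is not an extreme choice.

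**E.22, if it is restricted to FL-positive surfaces.** The same dye (s = 68.2%, f = 20%, q = 5%, r = 100%) gives a mean depth equal to the E.23 share times the mean depth of sub-surface tumour. The share is 0.190/0.2241 = 0.848. The reported mean is then 0.848 × 5 = 4.2 mm if tumour lies on average 5 mm down (assumed), and 8.5 mm if it lies 10 mm down. The figure follows the tumour's position.

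**E.24** has the same structure. No figure is given, because the documents do not say how often DCIS lies within or beyond 2 mm of ink.

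**The same dye under the repair.** The FL-positive fraction is f in every band below ink and f on carcinoma-free surfaces, so the excess is f − f = 0 at every depth.

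**The case against.** The strongest reply has five parts.

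1. E.22 has no numerator or denominator, and Section 15.1 defers detail to a SAP. This stands: the FL-positive restriction is explicit for E.23 and E.24 and is only one reading of E.22.
2. A reader might infer that nearly all six primary-specimen surfaces have carcinoma beneath them, so that every FL-positive surface supplies a depth and 58% is the expected reading. The documents do not support this. Section 5.1 says only that the specimen holds most or all of the tumour mass, and Section 12.6.1 provides for absence of carcinoma below a surface. Surfaces without the tumour type in question drop out of both endpoints. The 58% is an upper illustration.
3. Comparing with all carcinoma-free shaves would itself be biased, because FL-driven shaves are taken where the cavity or the opposing margin fluoresced. That would inflate the background and could hide real depth detection. This stands and shapes the fix.
4. The data are not complete for every surface. Arm 1 has no fluorescence review, Appendix 2 step 25 does not ask about the inside surface of FL-driven shaves although Section 12.4.3 does, and Section 12.6.1 does not call for a distance per tumour type. This also stands.
5. The endpoints are exploratory and descriptive, no depth claim is made in the protocol, and E.21 and E.27 report false positives separately. True, but those endpoints disclose the false-positive rate without correcting the depth figures.

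None of this removes the central point that co-occurrence on FL-positive surfaces cannot answer objectives 22 to 24.

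**Conclusion.** The point holds for E.23 and E.24, and for E.22 if tumour identified by fluorescence means tumour under FL-positive surfaces. Whenever some fluorescence is false and some of it falls over tumour with clear ink, a dye with no depth vision scores above 0%, and the score rises as specificity falls. That direction needs no assumed figure.

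The size does. With 70% detection at ink, carcinoma at ink on 5% of surfaces and 5% false positives, E.23 reads about 29% to 58% as the share of ink-negative surfaces with invasive carcinoma below goes from 30% to 100%. Over all the assumed inputs tried, it ran from 8% to 85%. The effect should be largest on primary-specimen surfaces and smaller on thin shaves.

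It would be wrong to infer that the trial's main conclusions are affected. P(1.1) and the key secondary tests do not use these endpoints. The consequence is confined to statements about depth of visualisation.

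**What to change.** 1. Use all Arm 2 ex vivo surfaces with a recorded fluorescence status, positive and negative. Report the FL-positive fraction by recorded distance to carcinoma: at ink, >0–2 mm, >2–5 mm, >5 mm, none. Allow for clustering by patient.
2. Split by invasive carcinoma and DCIS only where one type is present, or where distance is recorded per type.
3. Take the background rate from carcinoma-free surfaces not selected by fluorescence: carcinoma-free SoC shaves and primary-specimen surfaces with no carcinoma below. Exclude FL-driven shaves. Note that SoC shaves come from suspicious sites.
4. Claim visualisation at a depth only where the fraction exceeds that background.
5. Relabel E.22 to E.24 as *distance to nearest carcinoma beneath FL-positive surfaces*.

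The cost is a little programming, since Sections 12.4.3 and 12.6.1 already call for the fluorescence status and, where carcinoma is present, the distance. A split by type in mixed tumours would need distance recorded per type. The likely downside for the sponsor is a less favourable depth figure.
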